15.5. Appendix 5: Data Display Standards & Handling Conventions

15.5.1. Reporting Process

Software	

 The currently supported versions of SAS software and S-Plus will be used. 	
Reporting Area	
HARP Server	: uk1salx00175
HARP Compound	: /arenv/arprod/gsk1278863/mid201753/final_01
QC Spreadsheet	: /arenv/arprod/gsk1278863/mid201753/final_01/documents
Analysis Datasets	

 Analysis datasets will be created according to CDISC standards (SDTM IG Version 3.1.3 & ADaM IG Version 1.0. If the Study Data Standardization Plan (SDSP) exists for a study, ensure the CDISC versions are consistent. 	
Generation of RTF Files	

 RTF files will not be generated. 	

15.5.2. Reporting Standards

General	

 The current GSK Integrated Data Standards Library (IDSL) will be applied for reporting, unless otherwise stated (IDSL Standards Location: https://spope.gsk.com/sites/IDSLLibrary/SitePages/Home.aspx): 
 4.03 to 4.23: General Principles 5.01 to 5.08: Principles Related to Data Listings 6.01 to 6.11: Principles Related to Summary Tables 7.01 to 7.13: Principles Related to Graphics Do not include subject level listings in the main body of the GSK Clinical Study Report. All subject level listings should be located in the modular appendices as ICH or non-ICH listings 	
Formats	

 GSK IDSL Statistical Principles (5.03 & 6.06.3) for decimal places (DP's) will be adopted for reporting of data based on the raw data collected, unless otherwise stated. Numeric data will be reported at the precision collected on the eCRF. The reported precision from non eCRF sources will follow the IDSL statistical principles but may be adjusted to a clinically interpretable number of DP's. 	
Planned and Actual Time	

 Reporting for tables, figures and formal statistical analyses: 
 Planned time relative to dosing will be used in figures, summaries, statistical analyses and calculation of any derived parameters, unless otherwise stated. The impact of any major deviation from the planned assessment times and/or scheduled visit days on the analyses and interpretation of the results will be assessed as appropriate. Scheduled visits outside the protocol defined time-windows (i.e. recorded as protocol deviations) will be included in listings, figures, summaries and statistical analyses. Reporting for Data Listings: 
 Planned and actual time relative to study drug dosing will be shown in listings (Refer to IDSL Statistical Principle 5.05.1). Unscheduled or unplanned readings will be presented within the subject's listings. 	

Unscheduled Visits	

 Unscheduled visits will not be included in summary tables and/or figures. 
 If unscheduled visits are included, details of how summaries will be displayed will be provided in the RAP. All unscheduled visits will be included in listings. 	
Descriptive Summary Statistics	
Continuous Data	Refer to IDSL Statistical Principle 6.06.1: This does not apply to the output of statistical models or when the standard list is inappropriate. For cases where the standard may not be applied, see the display details in Section 6 to Section 10.
Categorical Data	N, n, frequency, %
Graphical Displays	

 Refer to IDSL Statistical Principals 7.01 to 7.13. 	

15.5.3. Reporting Standards for Pharmacokinetic

Pharmacokinetic Concentration Data	
PC Windows Non-Linear (WNL) File	PC WNL file (CSV format) for the non compartmental analysis by Clinical Pharmacology Modelling and Simulation function will be created according to GUI_51487. Note: Concentration values will be imputed as per GUI_51487
Descriptive Summary Statistics, Graphical Displays and Listings	Refer to IDSL PK Display Standards. Refer to IDSL Statistical Principle 6.06.1. Note: Concentration values will be imputed as per GUI_51487 for descriptive summary statistics/analysis and summarized graphical displays only.
Pharmacokinetic Parameter Derivation	
PK Parameter to be Derived by Programmer	The following PK parameters will be derived by the Programmer: 
 Dose Normalized PK parameters
Pharmacokinetic Parameter Data	
Is NQ impacted PK Parameters Rule Being Followed	Yes, refer to [Standards for Handling NQ Impacted PK Parameters].
Descriptive Summary Statistics, Graphical Displays and Listings	Each pharmacokinetic parameter (AUC(0-4), Cmax, and Tmax) will be summarized using the minimum set of summary statistics (IDSL statistical display principle 6.06.1). For each pharmacokinetic parameter (AUC(0-4), Cmax, and Tmax), the log-transformed parameter will be summarized using the summary statistics. The summary statistics are: N, n, geometric mean, 95% CI of geometric mean, standard deviation (SD) of log-transformed data and between subject coefficient of variation (CVb (%)) will be reported. [1] $CV_b (\%) = \sqrt{(\exp(SD^2) - 1) * 100}$ (SD = SD of log transformed data)

15.6. Appendix 6: Derived and Transformed Data

15.6.1. General

Multiple Measurements at One Analysis Time Point

 Subjects having both High and Low values for Normal Ranges at any post-baseline visit for safety parameters will be counted in both the High and Low categories of “Any visit post-baseline” row of related summary tables. This will also be applicable to relevant PCI summary tables. For multiple measurements at Screening and/or Day 1 visit, the screening pass visit record will be used for analysis (See Appendix 3: Assessment Windows)
Study Day

 Calculated as the number of days from Randomization Date: 
 Ref Date = Missing → Study Day = Missing Ref Date < Randomization Date → Study Day = Ref Date - Randomization Date Ref Date ≥ Randomization Date → Study Day = Ref Date - (Randomization Date) + 1
Unique Subject ID

 All subjects have unique subject ID for analyses even if a subject was enrolled after rescreened. Tables/figures/listings will be produced based on unique subject ID. For a rescreened subject, the unique subject ID will be derived from the first-assigned subject number though he or she seems to have different subject numbers in eCRF by screening assessments.
Rescreening Subjects

 For rescreened subjects, data collected in screening-pass visit will be used for analysis. They may have multiple records at Screening and/or Day 1 visit, which associates with a screening-pass visit and screening failure visit(s) Regarding a listing of SAEs in screening period, all pre-therapy SAEs captured in eCRF will be provided including screen failure records of rescreened subjects.
Treatment Start Date

 First randomized treatment start date
Treatment Stop Date - Daprodustat

 Calculated as the latest treatment stop date.
Treatment Stop Date – Epoetin Beta Pegol

 Following definition will be based on “assumed” treatment stop date because the treatment stop date is not captured in eCRF. 
Definition:
 
 If a subject has completed the treatment period (i.e., Week 52 visit record is present), treatment stop date will be calculated as Week 52 visit date.. 
 Week 52 visit date will be based on laboratory Hgb date. HemoCue Hgb date will be used when laboratory Hgb date is unavailable. If a subject has withdrawn from the treatment period (i.e., Week 52 visit record is missing), treatment stop date will be calculated as the latest dosing start date + XX days (1 day before the next treatment start date if a subject hadn’t withdrawn) 
 Subjects will have every 2 weeks or every 4 weeks injection of epoetin beta pegol, therefore assumed treatment stop date could include “+ 13 or 27 days” to mimic every 2 weeks or every 4 weeks dosing.

Subgroup definition
 
 For general considerations, see Section 5.4.2 Regarding prior ESA type, prior ESA dose, and ERI, see Section 15.6.2 Baseline iron use = use or non-use of pre-therapy iron medications (including ferric citrate (trade name Riona), see Section 15.6.3). History of diabetes will be derived from the current history diabetes (Yes/No) in medical history records. CKD stage will be derived from the eGFR measurement at a screening visit Cohort will be derived from the randomization number. 
 Cohort 1 = Randomization Number in PPD Cohort 2 = Randomization Number in PPD Cohort 3 = Randomization Number in PPD Dialysis will be derived from the randomization number. 
 ND subjects = Cohort 1 or 3 PD subjects = Cohort 2

Time Definitions (per GSK standard principles)
 
 1 week = 7 days 1 month = 30.4375 days 1 year = 365.25 days

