15. APPENDICES

15.1. Appendix 1: Protocol Deviation Management and Definitions for Per Protocol Population

15.1.1. Exclusions from Per Protocol Population

A subject meeting any of the following criteria will be excluded from the Per Protocol population:

Number	Exclusion Description
01	Informed Consent in Deviation Category
02	Eligibility Criteria Not Met in Deviation Category
03	Not Withdrawn After Developing Withdrawal Criteria in Deviation Category
04	Wrong study treatment or assignment administered in Deviation Subcategory
05	Randomization procedures (e.g. subject assigned to wrong stratum or subject randomized out of order) in Deviation Subcategory
06	Less than 3 out of 4 scheduled evaluable Hgb values from the primary efficacy evaluation period ¹
07	Subject received prohibited medication for more than 14 days during study period ²
08	Non-compliance with randomized medication (compliance category of under compliant or over compliant) ³ during the primary efficacy evaluation period, based on eCRF randomized medication exposure and compliance forms

NOTES:

[1] Evaluable Hgb values are described in Section 15.6.3.

[2] Prohibited medications include strong inhibitors of CYP2C8 (e.g. gemfibrozil) and strong inducers of CYP2C8 (e.g. rifampin/rifampicin), not include erythropoietin (e.g., epoetin/ darbepoetin alfa/ epoetin beta pegol, excluding epoetin beta pegol supplied by GSK).

[3] See Section 15.6.2; Under compliant: <80%, compliant ≥80% and ≤120%, over compliant >120%

CONFIDENTIAL

201753

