15.4.1.1. Study Phases for Hgb Data

Treatment State	Definition
Pre-therapy	Date \leq Randomization Date
On-therapy	Randomization Date $<$ Date \leq Treatment Stop Date + 1 day
Post-therapy	Date $>$ Treatment Stop Date + 1 day

NOTES:

- If randomization date is missing then the assessment will be considered to be pre-therapy

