
 The following scatter plot figures will be produced for overall: 
 Mean Dose during Week 40 to 52 vs. Baseline Body Weight (kg) Mean Dose during Week 40 to 52 vs. Baseline Hgb Mean Dose during Week 40 to 52 vs. Prior ESA dose Different displays by prior ESA use will be used to differentiate them. Vertical axis will indicate the mean dose (mg), horizontal axis will indicate the covariates of interest; baseline body weight (kg), baseline Hgb (g/dL), or prior ESA dose (IU/week). Mean dose will be calculated from the arithmetic mean using the latest 3 exposure records (i.e., for completers Week 40, 44, and 48), which are based on the actual doses and the scheduled visits. Subjects who has less than 3 dosing records will be excluded from the figures. Mean dose during Week 40 to 52 will also be summarized and listed. Only individual plots will be provided unlike the scatter plot of Hgb assessments.

Time in Target Range																																			
Time (weeks and percentage) in Target Range During the Primary Efficacy Evaluation Period																																			

 For this reporting purpose, on-therapy Hgb values of central laboratory during Week 40 to Week 52, including unscheduled visits, will be used. However, if a central laboratory Hgb value is missing, a corresponding non-missing HemoCue Hgb value, which is associated with the identical subject number and visit, will be used. Number of days that a subject's Hgb is within the analysis range of 11.0-13.0 g/dL inclusive between Week 40 and 52, including any on-therapy Hgb values that were taken during this time period. Linear interpolation is used to estimate Hgb between visits, if a subject has an intermittent missing value (Rosendaal1993). 																																			
Illustration of calculation																																			

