
NC: Not calculated, NA: Not available
 
 • Hgb laboratory assessment date will be used to calculate a duration (Ref Day) between assessments. 
 ○ Duration between assessments = [Hgb lab date] – [Hgb lab date of the previous measurement] 
If a subject has withdrawn from the treatment before Week 40 the duration between Week 40 to Week 52 cannot be calculated, the subject will not be included in a summary.
 
Basically, the duration should be [Week 52 lab date – Week 40 lab date] unless a subject has withdrawn before Week 52. In the case of withdraw before Week 52, Treatment Stop Date (see Section 15.6.1) will be used instead of Week 52.
 
 • As an above example, suppose a subject has Hgb reading 9.9 g/dL on August 1st (Week 40), then reading if 11.2 g/dL on September 1st. The assumption is made that the week, between these scheduled assessments the subjects Hgb increases from 9.9 to 11.2 g/dL in a linear manner, To following steps are taken to calculate the time (days) the subject’s Hgb was within target range (11.0 to 13.0 g/dL). 
 1. Calculate amount of Hgb shift (9.9 to 11.2 = 1.3 shift) and Hgb shift within range (0.2 out of shift is within range of 11.0 – 13.0) 2. Calculate percent of total shift (%) within range (0.2/1.3 = 15.38%) 3. Estimate the number of weeks since last visit within range (15.38% x duration between assessments = 15.38% x 31/7 weeks = 0.68 weeks within range) 
If a subject has an intermittent missing Hgb assessment (on-therapy), the linear interpolation will be done by ignoring missing Hgb data.
 
To calculate overall time (weeks) in Hgb target range, the total days in range for each time period are added together and divided by 7.
 
The % of time in range between Week 40 and Week 52 for a subject will be calculated by calculating overall time (weeks) within range and dividing by the total duration (weeks) between Week 40 to Week 52. Similarly, the % of time above Hgb target range and % of time above and below Hgb target range will be calculated,

Time (days) to reach the lower Hgb target (11.0 g/dL)

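### Different stop-date rules for completers mean that, of the two randomized arms, only daprodustat can lose its Week 52 Hgb from the on-therapy secondary and supplementary analyses

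*SAP*

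**What the plan says.** SAP 15.4.1.1 classes an Hgb value as on-therapy up to "Treatment Stop Date + 1 day" and as post-therapy after that. The limit is the same in both arms, but the stop date that feeds it is not (SAP 15.6.1):

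- **Epoetin beta pegol, Week 52 record present:** "treatment stop date will be calculated as Week 52 visit date", and "Week 52 visit date will be based on laboratory Hgb date", with the HemoCue date as fallback. The stated reason for an assumed date is "because the treatment stop date is not captured in eCRF".
- **Daprodustat:** "Calculated as the latest treatment stop date". Nothing links it to the Week 52 visit.

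The on-therapy label decides what enters several results:

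- Evaluable Hgb (15.6.3) is restricted to on-therapy values. It feeds the supplementary MMRM in 7.1.6.1 and Per Protocol criterion 06 in 15.1.1, which excludes subjects with "Less than 3 out of 4 scheduled evaluable Hgb values from the primary efficacy evaluation period".
- For time in target range (15.6.3), "on-therapy Hgb values of central laboratory during Week 40 to Week 52, including unscheduled visits, will be used". The denominator runs from the Week 40 to the Week 52 laboratory date "unless a subject has withdrawn before Week 52".
- The summaries of Hgb <7.5 g/dL, Hgb >13.0 g/dL and a rise of more than 2.0 g/dL over 4 weeks (7.3.2) also use on-therapy values.

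For the ITT population, 7.3.2 plans a treatment difference with 95% CI for time in range and an odds ratio with 95% CI for the >2.0 g/dL rise.

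**The concern.** The same scheduled visit can be kept in one randomized arm and dropped in the other, and the cause is how the stop date is derived. In the epoetin arm the Week 52 Hgb is compared with its own date and cannot fail. In the daprodustat arm it is compared with a separately recorded date and can.

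For an affected daprodustat completer, time in range can be understated, and a Week 52 excursion (<7.5, >13.0 or a >2.0 g/dL rise) goes uncounted. Neither can happen to an epoetin completer. The planned time-in-range difference and the odds ratio for the rise could therefore carry an artefact that depends on the arm. The time-in-range rule makes it worse: a completer has not withdrawn, so the last interval leaves the numerator but stays in the denominator.

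**Working it through.** **1. Phase of the Week 52 Hgb.** Let lag = Week 52 Hgb date − Treatment Stop Date. The value is on-therapy if lag ≤ 1 (15.4.1.1).

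| Completer | Lag 0 | Lag 1 | Lag 2 or more |
|---|---|---|---|
| Epoetin beta pegol | on-therapy | cannot occur | cannot occur |
| Daprodustat | on-therapy | on-therapy | post-therapy |

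**2. The SAP's worked time-in-range example (15.6.3).** Inputs: Hgb 9.9 on day 0, 11.2 on day 31, Week 48 missing, 13.4 on day 92.

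- 31 × 0.2/1.3 = 4.77 days; 61 × 1.8/2.2 = 49.91 days; sum 54.68 days.
- 54.68/92 = 59.43%. The SAP prints 59.42% because it rounds to 7.81 weeks first. The figure is reproduced.

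Now treat the Week 52 value as post-therapy:

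- Only 4.77 days remain. With the written 92-day denominator, 4.77/92 = 5.2%. With the denominator cut to the last usable Hgb, 4.77/31 = 15.4%.
- The 13.4 g/dL value no longer counts as an excursion above 13.0.
- With Week 48 also missing, 2 of 4 values remain, which meets Per Protocol criterion 06.

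**3. A completer at 12.0 g/dL at Weeks 40, 44, 48 and 52, nominal spacing.**

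- Week 52 kept: 84/84 = 100%.
- Week 52 dropped, written denominator: 56/84 = 66.7% in range, 0% above and 0% below. The other 28/84 = 33.3% is in no category.
- Week 52 dropped, denominator cut to Week 48: 56/56 = 100%.
- Range over the ±5-day windows with the written denominator: lowest 46/84 = 54.8% (Week 40 late by 5, Week 48 early by 5, Week 52 late by 5); highest 66/84 = 78.6% (the reverse).

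**4. Arm mean.** The SAP gives no frequency, so the affected share p is an assumption. At nominal spacing the largest loss per subject is 33.3 points, and the largest fall in the mean is p × 33.3:

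| Assumed p | Largest fall in daprodustat mean |
|---|---|
| 2% | 0.7 points |
| 5% | 1.7 points |
| 10% | 3.3 points |

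These are ceilings. A subject out of range from Week 48 to 52 loses nothing, and one partly in range loses less.

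**5. Per Protocol criterion 06.** Losing Week 52 alone leaves 3 of 4 evaluable values, which passes. Exclusion needs a second missing or non-evaluable value.

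**The case against.** The strongest case against has five parts.

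- **The stop date need not be the last tablet.** The SAP refers to the latest treatment stop date, and 0 mg records carry their own durations in the dose-adjustment illustration. The compliance formula in 15.6.2 counts planned tablets up to the dosing stop date, which fits a record-period date at least as well. Missed final tablets then need not open a gap. This stands: the point holds only for the recorded stop date, and how often it precedes the visit by 2 or more days is unknown.
- **The asymmetry has a reason.** The epoetin stop date is not collected, and with dosing every 4 weeks Week 52 is nominally the end of the last interval. This explains the epoetin rule, and the time since the last injection is no anomaly. It does not explain why daprodustat completers have no matching provision.
- **The denominator wording is loose.** The SAP introduces it with a qualifier and does not address a completer whose Week 52 value is unusable. This stands: 66.7% is the literal reading, and a cut denominator gives 100%.
- **Non-evaluable values are handled under missing at random.** In the evaluable-Hgb MMRM, Weeks 40 to 48 still inform Week 52. This softens the effect there, but not in time in range or the excursion counts.
- **No confirmatory result is shown to be affected.** A reader might infer that the non-inferiority test or the responder analysis loses Week 52 data. The text of 7.1.5 and 7.2 does not restrict either to on-therapy Hgb, so the SAP does not support that. The Hgb flowchart in 15.6.3 is not shown in the available text; the statements here rest on the written restrictions.

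**Conclusion.** The asymmetry is real and follows from 15.4.1.1 and 15.6.1 as written. Among the randomized non-dialysis completers, only daprodustat subjects can have the Week 52 Hgb reclassified as post-therapy, and no visible text restores it. The peritoneal dialysis cohort follows the same daprodustat rule but has no comparator.

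The reach is limited to the supplementary evaluable-Hgb MMRM, the Per Protocol count, time in range and the three Hgb excursion summaries. Two of these carry between-arm estimates, so the point is worth correcting, but it does not threaten the primary conclusion.

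Two stronger readings are not supported. One is that daprodustat time in range will be biased down: that depends on an unstated number of subjects, and the figures in step 4 are upper bounds at nominal spacing, under assumed frequencies and the literal denominator. The other is that affected subjects leave the Per Protocol set: losing Week 52 alone does not exclude anyone.

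**What to change.** - **SAP 15.4.1.1:** add one Hgb-phase rule for both arms. For subjects who completed the treatment period, the scheduled Week 52 Hgb is on-therapy. Do not extend this to subjects who permanently discontinued study treatment earlier but still attended; a rule triggered by the mere presence of a Week 52 record would sweep them in.
- **SAP 15.6.3, time in target range:** end the denominator at the last Hgb used in the numerator, so that time within, above and below range sums to 100%.
- Leave the stop dates for adverse events and exposure unchanged.

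The cost is a sentence or two of SAP text and a small change to two derivations, with no new data. The downside is that a few daprodustat Hgb values taken some days after the last recorded dosing date would count as on-therapy, as already happens for epoetin.

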Change from baseline in average oral iron dose (See Section 15.6.3) will be summarized using mean, standard deviation, minimum, P25, median, P75, and maximum. Quarter 1 (Day 1 to Week 12), Quarter 2 (Week 12 to Week 24), Quarter 3 (Week 24 to Week 40), Quarter 4 (Week 40 to Week 52), and whole treatment period will be used and Quarter 4 represents the primary efficacy evaluation period. For the ITT population, the treatment differences (daprodustat – epoetin beta pegol) and the associated 95% CIs will also be provided.

Number (%) of subjects who use iron during the treatment period and the primary efficacy evaluation period

The number and percentage of subjects who use iron during the screening period as baseline, the treatment period, and the primary efficacy evaluation period will be summarized separately. These will be also summarized by baseline iron use defined in Section 5.4.2

- **Iron Parameter (ferritin, TSAT, hepcidin, serum iron, and TIBC)**

Based on literature review the distributions of TSAT and hepcidin are skewed and require a log-transformation (See Section 5.2).

Raw observed value at each assessment visits

Ferritin, serum iron, and TIBC values will be summarized by treatment group using mean, standard deviation, 95% CI, minimum, P25, median, P75, and maximum at each assessment visit. TSAT and hepcidin values will be summarized by treatment group using geometric mean, standard error, coefficient of variation, and 95% CI based on log-transformed parameters, median, minimum, and maximum based on original scale at each assessment visit. Graphical summaries will also be provided for each iron parameter. These will be also summarized by baseline iron use, prior ESA use.

Change from baseline at each assessment visit

Change from baseline in ferritin, serum iron, and TIBC values will be summarized by treatment group using mean, standard deviation, 95% CI, minimum, P25, median, P75, and maximum at each assessment visit. Percent Change from baseline in TSAT and hepcidin values (Section 5.2) will be summarized by treatment group using geometric mean, coefficient of variation, and 95% CI based on log-transformed parameters, minimum, median, and maximum based on original scale at each assessment visit.

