15.4.1.3. Study Phases for Concomitant Medication

Treatment State	Definition
Pre-therapy	Concomitant medications that meet either following conditions will be regarded as pre-therapy. 
 • Concomitant Medication Start Date $<$ Randomization Date [a, b, c, j, n] • Concomitant Medication Start Date is missing [g, h, i, m, o] • Randomization Date is missing
On-therapy	Concomitant medications that meet either following conditions will be regarded as on-therapy. 
 • Randomization Date \leq Concomitant Medication Start Date \leq Treatment Stop Date + 1 [d, e, k, p, q, r, s, v] • (Concomitant Medication Start Date $<$ Randomization Date) AND (Randomization Date \leq Concomitant Medication Stop Date) [b, c, n]

Treatment State	Definition
	
 • (Concomitant Medication Start Date < Randomization Date) AND (Concomitant Medication Stop Date is missing) [j] • (Concomitant Medication Start Date is missing) AND (Concomitant Medication Stop Date ≥ Randomization Date) [h, i, o] • (Concomitant Medication Start Date is missing) AND (Concomitant Medication Stop Date is missing) [m]
Post-therapy	
Concomitant medications that meet either following conditions will be regarded as post-therapy.
 
 • Concomitant Medication Stop Date > Treatment Stop Date [c, e, f, l, r, t, v] • Concomitant Medication Stop Date is missing [j, k, l, m, s, u]

NOTES:

- Data of concomitant medication includes anti-hypertensive medication, ESA, iron, and blood products and blood supportive care products.
- Alphabets in brackets after the conditions correspond to each case in following illustrations.

Illustrations of the pre-therapy, on-therapy, and post-therapy for concomitant medications are included below:

	Pre-therapy	On-therapy		Post-therapy		Pre-therapy medication	On-therapy medication	Post-therapy medication
(a)	x—x					Y	N	N
(b)	x—		—x			Y	Y	N
(c)	x—		—			Y	Y	Y
(d)			x—x			N	Y	N
(e)			x—			N	Y	Y
(f)						N	N	Y
(g)	?—x					Y	N	N
(h)	?—		—x			Y*	Y	N
(i)	?—		—			Y*	Y*	Y
(j)	x—		—			Y	Y**	Y**
(k)			x—			N	Y	Y**
(l)						N	N	Y
(m)	?—		—			Y***	Y***	Y***
(n)	x—	x				Y	Y	N
(o)	?—	x				Y*	Y	N
(p)		x	—x			N	Y	N
(q)		x	—			N	Y	N
(r)				x		N	Y	Y
(s)				x		N	Y	Y**
(t)					x	N	N	Y
(u)					x	N	N	Y
(v)			x—		x	N	Y	Y

x = start/stop date of medication
 ? = missing start/stop date of medication

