- A Quarter End Date will be replaced with Treatment Stop Date (see Section 15.6.1) when treatment start date at Week 12, 24, or 40 is missing (i.e. early withdrawal before Week 12, 24, or 40). In this case, the subsequent Quarter(s) will not be generated.
- Iron medication start/stop date will be defined newly for the analyses in addition to Quarter start/end date to derive amount of iron dose within a specified Quarter (analysis flags may be used to judge which quarters the iron records should belong to).

[1] Quarter 4 represents the primary efficacy evaluation period.

- If iron medication start date < screening date, the iron medication start date will be replaced with screening date for the analysis.
- If iron medication stop date > Treatment Stop Date, the iron medication stop date will be replaced with Treatment Stop Date for the analysis.
- If iron medication start date and stop date step over quarters, the iron medication record will be divided; the end date in the former of divided record and the start date in the latter of divided record will be the former quarter end date and the latter quarter start date, respectively.
- If no start or stop date is recorded on iron medication, the date will be replaced with Screening Date or Treatment Stop Date, respectively.
- For ferric citrate (trade name: Riona, GSK drug code = 00752601), iron dose value for analyses will be converted as follows,
 - Iron dose for analyses (mg) = iron dose (mg) x 62 / 250

TIBC

- TIBC will be calculated automatically by the central laboratory using:
 - $TIBC = UIBC + \text{total iron}$

TSAT

- Based on literature review the distribution of TSAT is skewed and requires a log-transformation. Calculation of statistics on log-transformed data are described in Section 5.2.
- TSAT will be calculated automatically by the central laboratory using:
 - $TSAT = 100 * (\text{Serum Iron}/TIBC)$

Hepcidin

- Based on literature review the distribution of hepcidin is skewed and requires a log-transformation. Calculation of statistics on log-transformed data are described in Section 5.2

Iron Use Subgroup

- The baseline iron use will be defined as a subject takes a pre-therapy iron medication excluding sucroferric oxhydroxide (trade name: P-TOL, GSK drug code = 54909401).

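### Baseline Iron Use is defined by any pre-therapy iron record, whereas baseline iron use and dose refer to the screening period and rest on on-therapy records only

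*SAP*

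**What the plan says.** The subgroup is defined twice in the SAP. Section 15.6.1 (Subgroup definition) has "Baseline iron use = use or non-use of pre-therapy iron medications", with ferric citrate counted as iron. Section 15.6.3 (Iron Use Subgroup) has "The baseline iron use will be defined as a subject takes a pre-therapy iron medication excluding sucroferric oxhydroxide". Neither gives a time window.

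The term pre-therapy comes from Section 15.4.1.3, which covers iron: "Data of concomitant medication includes anti-hypertensive medication, ESA, iron, and blood products and blood supportive care products". A record is pre-therapy if it started before randomization, if its start date is missing, or if the randomization date is missing. The illustration there marks cases (a) and (g), both stopped before randomization, as pre-therapy.

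For the iron endpoints, baseline means something narrower. Section 7.3.2 summarizes "The number and percentage of subjects who use iron during the screening period as baseline, the treatment period, and the primary efficacy evaluation period", and it also takes the screening period as baseline for oral iron dose. The window table in 15.6.3 (Oral Iron Dose by Quarter) sets baseline from Screening Date to Randomization Date - 1.

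Section 15.6.3 adds a record-selection rule. Iron users are subjects with an on-therapy iron record, and the dose calculations use on-therapy records. Under 15.4.1.3, a record that stopped before randomization is not on-therapy.

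**The concern.** The word baseline carries three meanings in one family of displays: any iron started before randomization (the subgroup), the screening window (the stated baseline), and on-therapy records (the data allowed into the calculation). They meet in Tables 2.84 and 2.85 (oral iron dose by baseline iron use) and Tables 2.88 and 2.89 (iron use by baseline iron use). There, a subject can sit in the Yes stratum while the baseline row of the same table shows no use and 0 mg.

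The same stratum is used for the iron-parameter subgroup tables (2.110 to 2.129), the iron-parameter MMRM repeated by subgroup (7.3.5.1), and the figures by baseline iron use (2.48 to 2.57 and 2.68 to 2.77). At stake is whom the Yes stratum describes and whether its baseline use and dose are reported correctly.

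**Working it through.** No sample size, power or error-rate figure depends on this point, so there is no figure of the plan to reproduce. The check applies the SAP's date rules to constructed iron records.

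**Inputs**
- Randomization = day 0.
- Screening = day -28. This is an assumption, taken from the 4-week screening phase in Section 2.3.
- Pre-therapy (15.4.1.3): start < 0 or start missing.
- On-therapy for a record that started before randomization or has a missing start (15.4.1.3): stop ≥ 0 or stop missing.
- Screening-period use (7.3.2; 15.6.3 window): start missing or ≤ -1, and stop missing or ≥ -28.
- Days in the baseline window: min(stop, -1) - max(start, -28) + 1. Section 15.6.3 moves starts earlier than screening, and missing starts, to the screening date.

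**Results**

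| Record | Start, stop (day) | Subgroup | Screening-period use | On-therapy record | Days in window |
|---|---|---|---|---|---|
| A: stopped about 2 years before screening | -1000, -758 | Yes | No | No | -758 + 28 + 1 = -729 |
| B: stopped 60 days before screening | -200, -88 | Yes | No | No | -88 + 28 + 1 = -59 |
| C: start missing, stopped 60 days before screening | missing, -88 | Yes | No | No | -88 + 28 + 1 = -59 |
| D: stopped during screening | -100, -10 | Yes | Yes | No | -10 + 28 + 1 = 19 |
| E: ongoing past Day 1 | -100, 50 | Yes | Yes | Yes | -1 + 28 + 1 = 28 |

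**Reading the table**
- Records A to C are subgroup Yes without any iron in the screening window. The negative durations show that the start-date replacement was not written for such records. The on-therapy rule drops them, so the baseline dose is 0 mg.
- Record D covers 19 of the 28 screening days, yet it is not an on-therapy record. Read literally, 15.6.3 gives it 0 mg at baseline and does not count the subject as an iron user, although 7.3.2 would.
- Record E agrees on every definition.

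Two separate mismatches follow. One is the missing look-back limit in the subgroup (A to C). The other is the record-selection rule for baseline use and dose (D). Correcting only the first would leave the second.

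**The case against.** The strongest objection is that nobody may be affected by the first mismatch. The SAP does not say how far back the eCRF iron form collects, and it has no handling rule for records that ended before screening, which fits authors who expected none. The wording "The baseline iron use will be defined as a subject takes a pre-therapy iron medication" uses the present tense and could be read as current use. This stands as a limit on size. It does not settle the definition, because the term it relies on is defined in 15.4.1.3 to include ended records, and 15.6.1 lacks even that nuance. Nor does it touch record D, which needs no history before screening.

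A reader might also infer that past users dilute a comparison of iron users with non-users, or inflate later iron use in the Yes stratum. The SAP does not support either. Section 7.3.5.1 plans daprodustat against epoetin beta pegol within each subgroup, with no user versus non-user contrast and no interaction test. Past users who stay off iron would lower later use in the Yes stratum, so the direction is not certain. Change from baseline in oral iron dose (Tables 2.82 and 2.83) is not displayed by this subgroup.

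Finally, Section 5.4.2 confines the subgroup to iron analyses, and Section 5.5 treats other secondary endpoints as complementary or exploratory. That is correct and sets the priority.

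**Conclusion.** The point holds as a definitional inconsistency in the secondary iron analyses. Under the SAP's own rules the Yes stratum can include subjects with no iron in the screening period, and its baseline use and dose can be understated. Understatement arises from past users placed in the stratum and from screening-period users whose records are not on-therapy.

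The size cannot be computed. It depends on the eCRF look-back, which is not given, and on how many subjects stopped iron during screening. For those who stopped before screening, the number may be zero.

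It would go too far to conclude that treatment effects are biased. Membership rests on iron started before randomization, or with a missing start date, under one rule for both arms. The randomized comparison within a stratum is therefore not biased; only the description of the stratum is affected. The primary and principal secondary analyses do not use this subgroup. Low priority.

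**What to change.** 1. In 15.6.1 and 15.6.3, define Baseline Iron Use as Yes only if an eligible iron record overlaps Screening Date to Randomization Date - 1. That means start missing or on or before Randomization Date - 1, and stop missing or on or after Screening Date. Ferric citrate stays included and sucroferric oxyhydroxide stays excluded. All other subjects are No.
2. In 15.6.3, state that pre-therapy records overlapping that window enter the baseline iron-use count and the baseline iron dose, and that on-therapy records are used only for the treatment period and the quarters.

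Applied to the five records, rule 1 gives No for A, B and C and Yes for D and E, which matches screening-period use in every case. Rule 2 then gives D its 19 days of baseline dose instead of 0 mg. The rules also agree with the existing replacement of a missing start by Screening Date and a missing stop by Treatment Stop Date.

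The cost is a few lines of SAP wording, one revised subgroup derivation and one revised record selection. No new data are needed.
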